6 HANDLING OF MISSING DATA

No replacement criterion for missing values will be used, except for dates, as appropriate.

- If the year is unknown, the date will not be imputed and will it be treated as a missing value.
- If the day and month are unknown, it will be imputed as July 1.
- If the day is unknown, the value of 15 will be assigned.

7 STATISTICAL ANALYSIS AND METHODOLOGY

7.1 STATISTICAL METHODS

The investigator will collect the data from the patients enrolled in an electronic Case

PFIZER CONFIDENTIAL

Report Form specially designed for this study.

The patient number assigned provide is a correlative number with no identification value.

All information will be stored in a database designed for the study that will be a true reflection of the case report form. Once the project is finished, the data will be transferred to SAS for the final validation and the statistical analysis.

A Data Management Plan (DMP) will be drawn up, and once it has been approved by the person in charge of the study, Queries will be programmed in the database.

7.2 STATISTICAL ANALYSIS

7.2.1. Included and evaluable population

The descriptive statistics of patients who meet all the inclusion criteria and none of the exclusion criteria will be presented.

In the subpopulation of non-evaluable patients, their frequency distribution will be presented, depending on the reasons for non-eligibility:

[figure not shown]
- Patients who are not 18 years of age or older and who have been treated for metastatic renal carcinoma with Sunitinib as first-line (prior cytokine treatment is admitted) between 2007 and October 30, 2018.
- Patients aged 18 years or older who have been treated for a metastatic renal carcinoma with Sunitinib as second line.
- Patients aged 18 years or older who have been treated for a metastatic renal carcinoma with Sunitinib as first line (prior cytokine treatment is admitted) between 2007 and October 30, 2018 and who have not obtained, as best response to treatment, total disease remission in the opinion of the treating physician from the clinical, radiological and/or macroscopic standpoint.
- Patients whose duration of CR has not been confirmed with at least 2 consecutive imaging tests, with no limit on the duration of this response.
- Patients treated with another drug other than Sunitinib.
- Patients without radiology reports that substantiate the CR.
- Patients without a record of the dose and regimen of Sunitinib.
- Patients who achieved complete remission after October 30, 2018.

7.2.2. Descriptive analysis

The mean value, standard deviation, median, minimum, maximum, interquartile range (RIQ) and 95% confidence interval (CI 95%) of the following variables will be provided:

- Age of the patients at the start of treatment.
- Pre-treatment necrosis percentage

PFIZER CONFIDENTIAL

[figure not shown]

- Laboratory data at the start of treatment:
 - Haemoglobin
 - Leukocytes
 - Corrected calcium
 - LDH levels
 - Lymphocytes
 - Platelets
 - Neutrophil/Lymphocyte rate
- Time elapsed from the nephrectomy to the start of systemic treatment
- Time on treatment until CR is reached
- Duration of CR
- Time on treatment after CR is reached

The frequency distribution of patients will be presented according to:

[figure not shown]
- ECOG:
 - 0
 - 1
 - 2
 - 3
 - 4
- KPS (Karnofsky Performance Status):
 - 0%
 - 10%
 - 20%
 - 30%
 - 40%
 - 50%
 - 60%
 - 70%
 - 80%
 - 90%
 - 100%
- Motzer prognostic criteria:
 - Favourable (0 factors)
 - Intermediate (1-2 factors)
 - Poor (3 or more factors)
- Heng prognostic criteria:
 - Favourable (0 factors)
 - Intermediate (1-2 factors)
 - Poor (3 or more factors)
- Comorbidities:

PFIZER CONFIDENTIAL

- Cerebrovascular disease
 - Liver disorders
 - Renal failure
 - Autoimmune disease
 - Chronic dermatological disease
 - Obesity
 - Bowel disease
- Metastasis site:
 - Lung
 - Liver
 - Brain
 - Pancreas
 - Nodes
 - Other
- Fuhrman grade:
 - I
 - II
 - III
 - IV
- TNM tumour stage
- Histological type:
 - Clear cell
 - Chromophobe
 - Sarcomatoid, percentage
 - <20%
 - 20-30%
 - 31-50%
 - 51-75%
 - >75%
 - Papillary type 1
 - Papillary type 2
 - Mixed
 - Not performed
- Previous nephrectomy:
 - Yes
 - No
- Complications during surgery:
 - Yes
 - No
- Initial dose and treatment regimen:

PFIZER CONFIDENTIAL

- Sunitinib 50 mg 4/2 regimen
- Sunitinib 50 mg 2/1 regimen
- Sunitinib 37.5 mg 4/2 regimen
- Sunitinib 37.5 mg 2/1 regimen
- Sunitinib 25 mg 4/2 regimen
- Sunitinib 25 mg 2/1 regimen

- Type of treatment received:

- Sunitinib monotherapy
- Sunitinib + subsequent local treatment
- Local treatment techniques for residual lesions:
 - Traditional surgery
 - Radiotherapy
 - SBRT

7.2.3. Follow-up analysis

The evolution of the following variables will be presented for each one of the predefined times for data collection:

- **Neutrophil/leukocyte rate** throughout treatment:

- Baseline
- At 6 weeks
- At 3 months
- At 6 months
- At 9 months
- At 12 months
- Subsequently, every 6 months in the available analyses close to these dates.

At all the time points when this analytical variable is gathered, the possible occurrence of significant changes in the neutrophil/lymphocyte rate versus the baseline (at the beginning of treatment) will be analysed. For this purpose, generalised linear mixed-effects models will be used over time as a fixed factor and the patient as a random factor.

- **Dose modifications during treatment with Sunitinib.** The absolute and relative frequencies of the number of patients who have had dose modifications since the start of treatment will be reported. In the subpopulation of patients with dose modifications, the frequency distribution with regard to the number of dose modifications will be presented:

- 1 modification:
 - Type of modification:
 - ✓ Increase
 - ✓ Reduction
 - ✓ Changes in the rest regimen
 - Reason for the modification:
 - ✓ Toxicity
 - ✓ Other different reasons)
 - New dose prescribed:
 - ✓ Sunitinib 50 mg 4/2 regimen

PFIZER CONFIDENTIAL

- ✓ Sunitinib 50 mg 2/1 regimen
- ✓ Sunitinib 37.5 mg 4/2 regimen
- ✓ Sunitinib 37.5 mg 2/1 regimen
- ✓ Sunitinib 25 mg 4/2 regimen
- ✓ Sunitinib 25 mg 2/1 regimen
- ✓ Other treatment regimen

- 2 modifications:
 - Type of modification:
 - ✓ Increase
 - ✓ Reduction
 - ✓ Changes in the rest regimen
 - Reason for the modification:
 - ✓ Toxicity
 - ✓ Other different reasons)
 - New dose prescribed:
 - ✓ Sunitinib 50 mg 4/2 regimen
 - ✓ Sunitinib 50 mg 2/1 regimen
 - ✓ Sunitinib 37.5 mg 4/2 regimen
 - ✓ Sunitinib 37.5 mg 2/1 regimen
 - ✓ Sunitinib 25 mg 4/2 regimen
 - ✓ Sunitinib 25 mg 2/1 regimen
 - ✓ Other treatment regimen

A summary calculation of the dose modifications will be made for the aspects described above.

- **Temporary dose interruption during treatment with Sunitinib.** The absolute and relative frequencies of the number of patients who interrupted the treatment will be reported. In the subpopulation of patients with treatment interruptions, frequency distribution will be presented for:
 - Number of treatment interruptions:
 - 1
 - 2
 - 3
 - 4
 - Reason for interruption:
 - Toxicity
 - CR. In this subgroup of patients:
 - Active participation by the patient in the decision to discontinue the product once CR is reached
 - At the patient's decision
 - At the doctor's decision
 - Other reasons
 - Calculation of total days of treatment interruption

A summary calculation of the dose modifications will be made for the aspects described above. For the calculation of total days of interruption of treatment, descriptive central tendency (mean, median) and dispersion (standard deviation, interquartile range)

PFIZER CONFIDENTIAL

statistics will be presented.

- **Post-treatment.** The absolute and relative frequency of the number of patients who discontinue first-line Sunitinib treatment will be reported definitively after the CR. In the subpopulation of patients who remain on second-line treatment, frequency distribution will be presented for:
 - o Reason for terminating the treatment:
 - Toxicity
 - Progression
 - Death, reason:
 - Progression
 - Toxicity, in this case:
 - ✓ In the investigator's opinion related to Sunitinib
 - ✓ Not related to Sunitinib
 - Another reason
 - o Total number of days of duration of treatment with second-line Sunitinib.
 - o Post-second-line Sunitinib pharmacological treatment group after disease progression after a period of CR:
 - TKI
 - mTOR
 - Immunotherapy

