6. STUDY RATIONALE

Complete response (CR) to a tyrosine kinase inhibitor (TKI) is reached infrequently in clinical trials for the treatment of metastatic renal cell carcinoma, where the classic description of CR contemplates only pharmacological treatment and this response is evaluated either by the study investigator or by a centralised radiological committee (most common situation).

Since the eradication of all measurable lesions will be reached in a small percentage of patients, the Summary of Product Characteristics for sunitinib does not provide guidelines regarding the therapeutic strategy to be followed in these cases, i.e. continuing the treatment and at which dose or to discontinue it definitively.

The objective of this registry is to shed light on this matter, reviewing what was done in these patients in order to draft useful recommendations for the clinician who faces this dilemma.

➤ Data from phase III clinical trials

In the sunitinib pivotal clinical trial (Motzer *et al.*, 2007), in the intermediate analysis and according to RECIST criteria, no patient reached CR to treatment by central radiological committee while there was one patient with CR in the opinion of the investigators, which accounted for less than 1% of the subjects who participated in the clinical trial. However, in the final analysis published 2 years later (Motzer *et al.*, 2009), 11 patients (3%) in the sunitinib arm achieved CR to treatment in the opinion of the investigator.

In the sorafenib clinical trial, TARGET study (Escudier *et al.*, 2007), there was no patient with CR by the independent committee in the intermediate analysis, while one CR case (<1%) was described by investigator.

In the phase III trial of pazopanib versus placebo (Sternberg *et al.*, 2010), there was one patient in the intermediate analysis who achieved CR to treatment with pazopanib (<1%) by the independent radiological committee

In the COMPARZ study (Motzer *et al.*, 2013), according to an independent radiological committee, 3 patients achieved CR to treatment with sunitinib versus 1 patient in the pazopanib treatment arm.

➤ Data from expanded-access programmes:

In the sunitinib expanded-access programme (Gore *et al.*, 2015) where the tumour response rate was evaluated by the investigators, 1% of patients achieved CR to treatment as best response.

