7. HYPOTHESIS AND OBJECTIVES

This study is a retrospective registry of cases of CR to treatment with sunitinib in patients with metastatic renal cell carcinoma and has a purely descriptive purpose. Therefore, no previous hypothesis has been established.

7.1. Primary objectives:

To describe complete responses in daily clinical practice in Spain between 2007 and 30 October 2018, such as the documented disappearance of all lesions in the investigator's opinion on at least 2 consecutive CT scans.

To look for associations between CR from a macroscopic point of view and the baseline characteristics of both the patient and the tumour, such as:

- Demographic characteristics (age at the start of treatment)
- Comorbidities: cardiac, renal, endocrine, autoimmune and liver.
- Previous nephrectomy

- Classification of the risk group according to Motzer and/or Heng criteria and the association between each prognostic variable, such as: baseline patient status, time from nephrectomy to systemic treatment start, presence of anaemia, corrected calcium, LDH levels, neutrophil levels and platelet levels.
- Tumour data: histology, Fuhrman grade, presence of tumour necrosis and number and location of metastases (organs involved).

7.2. Secondary objectives:

- **To establish recommendations** to be followed **in patients who obtain CR to sunitinib treatment** based on the case recording and the adopted therapeutic strategy that obtained the greatest clinical benefit.
- To define **the median time on treatment with sunitinib until lesion complete remission is reached in the patient responsible physician opinion.**
- To define **the median duration of CR.**
- The time elapsed from the confirmation of CR to disease stabilisation/progression or change of treatment due to unacceptable toxicity or death from any cause will be collected.
- **The dose and treatment regimens used will be recorded.** In the case of changes in the treatment dose (increase or reduction), the reason (toxicity, efficacy, decision taken after lesion elimination or upon request of the patient) will be specified.
- **Description of local treatment techniques** if they were used and at what time they were applied. In the case of a pathology report on the resected part, the percentage of necrosis and histology will be recorded, as well as the surgical complications in the case that they arose.

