2 INTRODUCTION

The purpose of this Statistical Analysis Plan (SAP) is to provide a detailed description of the statistical analyses that will be performed to generate the final report for the ATILA study. This includes a brief summary of the main study characteristics and the aim of the SAP, which refers to the statistical analysis plan for this study.

CR to a tyrosine kinase enzyme inhibitor (TKI) is rarely achieved in clinical trials for the treatment of metastatic renal carcinoma, where the classic description of CR only provides for pharmacological treatment, and this response is evaluated either by the study investigator or by a centralized radiological committee (most common situation).

Since the eradication of all measurable lesions will be achieved in a small percentage of patients, the Sunitinib summary of product characteristics does not provide guidelines on the therapeutic strategy to be followed in these cases, i.e. continue the treatment and at what dose or discontinue it indefinitely.

The purpose of this registry is to shed some light on this issue, reviewing what was done in these patients in order to write useful recommendations for the clinician facing this dilemma.

➤ Data from phase III clinical trials

In the Sunitinib pivotal clinical trial (Motzer et al., 2007), the interim analysis, and according to RECIST criteria, no patient achieved CR to treatment according to the central radiological committee, whereas according to the researchers there was one patient with CR, which meant less than 1% of the subjects who participated in the clinical trial. However, in the final analysis published 2 years later (Motzer et al., 2009), 11 patients (3%) in the Sunitinib arm reached CR to treatment according to the investigator.

In the Sorafenib clinical trial, TARGET study (Escudier et al., 2007), there was no patient with CR according to the independent committee in the interim analysis, while one case of CR was described by investigator (<1%).

In the phase III trial of Pazopanib versus placebo (Sternberg et al., 2010), there was one patient in the interim analysis who achieved CR to treatment with Pazopanib (<1%) according to the independent radiological committee.

In the COMPARZ study (Motzer et al., 2013), according to an independent radiological committee, 3 patients achieved CR to treatment with Sunitinib versus 1 patient in the Pazopanib treatment arm.

➤ **Data from expanded access programmes:**

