2.2 STUDY OBJECTIVES

Describe the complete responses in daily clinical practice in Spain in the 2007-October 30, 2018 period as the documented disappearance of all lesions in the investigator's opinion on at least 2 consecutive CT scans.

Seek associations between the CR from the macroscopic point of view and the baseline features of both patient and tumour, such as:

- Demographic characteristics (age at the start of treatment)
- Comorbidities: cardiovascular, renal, endocrine, autoimmune, intestinal, chronic dermatological, obesity, intestinal and hepatic.
- Previous nephrectomy
- Classification of the risk group according to Motzer and/or Heng criteria and of the association between each one of the prognostic variables, such as: patient baseline status, time elapsed from nephrectomy to the start of systemic treatment, presence of anaemia, corrected calcium, LDH levels, neutrophil and platelet levels.
- Tumour data: histology, Fuhrman grade, presence of tumour necrosis and number and location of metastases (organs involved).

PFIZER CONFIDENTIAL

The risk factors associated with the occurrence of CR from the macroscopic point of view will be sought.

SECONDARY OBJECTIVES

- *Develop recommendations to be followed in patients who obtain CR when treated with Sunitinib based on the case registry and the therapeutic strategy adopted that yielded the greatest clinical benefit.*
- *Define the median time of treatment with Sunitinib until complete remission of the lesions in the opinion of the patient's treating physician.*
- *Define the median duration of the CR.*
- *The time elapsed from the verification of the CR to disease to stabilisation/progression or change of treatment due to unacceptable toxicity or death from any cause will be collected.*
- *A record of the doses and treatment regimens used will be made. In the event of changes in the treatment dose (increase or reduction) the reason will be specified: toxicity, efficacy, decision taken after the disappearance of lesions or at patient's request.*
- *Description of local treatment techniques if used and when they were applied. In the pathological anatomy report of the resected piece, the percentage of necrosis and histology will be recorded, as will any surgical complications that presented.*
- *Safety profile of treatment with sunitinib: the highest grade adverse events presented by the patients will be recorded, as well as whether the treatment had to be discontinued at any point due to toxicity.*

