- Time on treatment with Sunitinib until complete remission of lesions, calculated as the difference between treatment start date and CR confirmation date (2nd CT scan).
- Duration of complete remission (DOR)
- Progression-free survival (PFS) or time from remission to disease progression, change of treatment due to unacceptable toxicity or death. It will be calculated as the time elapsed from the RC confirmation date (2nd CT scan) until the date of progression/death or change of treatment for unacceptable toxicity, as applicable, or else it will be censored on the date of the last patient follow-up.

Taking into account the asymmetry normally observed in the distribution of survival times and that follow-up periods may be uneven (different study entry date), the Kaplan-Meier method will be used to estimate the median time to CR together with its 95% confidence interval. The median will indicate when complete remission of the disease occurred in 50% of patients.

In order to find associations between time to CR and the baseline features of both patient and tumour, a log-rank test will be used for comparison between groups and the determination of the statistical significance of the correlation between each of the baseline variables and the time to complete remission of disease. The following baseline characteristics are considered:

[figure not shown]
- Demographic characteristics
- Comorbidities
- Tumour data
- Prior nephrectomy in the treatment of metastatic renal cancer
- Classification of the risk group according to Motzer and/or Heng criteria.
- Patient's baseline status, including ECOG grade, presence of anaemia, corrected calcium, LDH levels, neutrophil and platelet levels.

This analysis will establish which baseline characteristics are associated with a shorter complete response time to treatment.

As part of the secondary objectives, the doses and treatment regimens observed in the sample will also be descriptively summarised by means of absolute and relative frequencies. In the case of changes in the treatment dose, the frequency of patients with dose increase, dose reduction and changes in the rest regimen will be specified. Similarly, the most frequent reasons for changes in dosage and/or treatment regimen to RC will be reported.

Frequencies of the type of treatment received will be presented, depending on whether it

Pfizer Confidential

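### The SAP's dose-modification tables merge three of the four promised reasons for a change and show no dose or regimen after complete response

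*SAP*

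**What the plan says.** Both documents pose the same practical question. The SAP Introduction puts the choice after CR as whether to "continue the treatment and at what dose or discontinue it indefinitely"; Protocol Section 6 puts it as "continuing the treatment and at which dose or to discontinue it definitively". SAP Section 5 adds the aim of describing the strategy followed after macroscopic disease has gone, with a view to recommendations.

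On dose changes, SAP 2.2 commits that "the reason will be specified: toxicity, efficacy, decision taken after the disappearance of lesions or at patient's request". Protocol 7.2 says the same: "the reason (toxicity, efficacy, decision taken after lesion elimination or upon request of the patient) will be specified".

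SAP 7.2.3 then sets out the tables. For dose modifications, "The absolute and relative frequencies of the number of patients who have had dose modifications since the start of treatment will be reported". Patients are broken down into those with one and those with two modifications. Within each, the table gives the type of change, the new dose, and a reason that is either toxicity or "Other different reasons".

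SAP 7.2.4 returns to the topic. It gives frequencies of increases, reductions and rest-schedule changes with no time reference, and states that "the most frequent reasons for changes in dosage and/or treatment regimen to RC will be reported".

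**The concern.** A patient whose dose was cut early for toxicity and a patient whose dose was cut much later because scans had cleared are counted in the same table. The first appears under toxicity. The second falls into the residual row, together with changes made for efficacy or at the patient's wish. Yet the second is the kind of decision the registry was set up to describe. If the programmers follow SAP 7.2.3 as written, the report can state how many patients had a dose change at some point. It cannot state from that table what dose patients were on after CR, or how often CR itself prompted a change.

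**Working it through.** There is no stated figure to reproduce and no calculation of size or power involved. The check is a comparison of the objective, the tables and the data collected.

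**1. Reasons: objective against table**

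| Reason named in SAP 2.2 and Protocol 7.2 | Row in SAP 7.2.3 dose table |
|---|---|
| Toxicity | Own row |
| Efficacy | None; residual row |
| Decision prompted by disappearance of lesions | None; residual row |
| Patient's request | None; residual row |

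Reasons with their own row: 1 of 4. Reasons merged: 4 − 1 = 3.

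**2. Timing.** The dose table runs from treatment start and has no break at CR. SAP 7.2.2 tabulates the initial dose and regimen. The new dose in 7.2.3 is listed by number of modifications, not by its position relative to CR. Planned tables giving dose or regimen after CR: 0.

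**3. Contrast within SAP 7.2.3.** The interruption table makes CR a reason in its own right, asks whether patient or doctor decided, and allows up to four interruptions. The dose table has no CR reason and stops at two changes.

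**4. What is covered elsewhere.** The continue-or-stop part of the question has its own outputs: interruptions because of CR and definitive discontinuation after CR (7.2.3), time on drug following CR (7.2.2), and the reasons and patient involvement when treatment was stopped during maintained CR (7.2.4). The gap is confined to dose and regimen.

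**5. Whether the data allow a finer table.** SAP Section 5 lists, for each change, its date, its reason and the resulting dose, so a split at CR is feasible. Two matters affect it:

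- *The CR date.* SAP Section 5 dates CR at the first clear CT when defining time to CR; SAP 7.2.4 uses the second, confirmatory CT. A change made between the two scans would switch period depending on which is used.
- *Imputed dates.* SAP Section 6 sets an unknown day to the 15th and an unknown day and month to 1 July. The largest possible error is 31 − 15 = 16 days in the first case. In the second it is 30 + 31 + 30 + 31 + 30 + 31 = 183 days (1 July to 31 December). A change near CR could therefore land in the wrong period.

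**The case against.** Several points can be made for the plan as it stands.

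- *The dose objective does not itself ask for a split at CR.* This is correct. The split is inferred from the rationale and the aim in SAP Section 5. The four reasons, by contrast, are an explicit commitment.
- *SAP 7.2.4 promises the commonest reasons without restricting them to two rows.* It might recover some detail, so a reader should not infer that every CR-driven change would become unidentifiable. But the phrase about changes *to RC* is an imperfect translation. It could mean up to CR or because of CR, it names no categories, and it gives no dose after CR. It neither fills the gap nor proves that reasons after CR are excluded.
- *The residual reason line may be damaged.* It ends in an unmatched bracket in both places, so some wording may be missing. This tempers confidence, although both occurrences show the same two options.
- *Section 7.2.3 opens by promising results at predefined times.* The only times listed are those under the neutrophil ratio, counted from treatment start. In the single-centre series both documents cite, time to CR ranged from 2 to 28 months on drug alone and from 5 to 45 months with local treatment. Fixed times from treatment start cannot separate the periods before and after CR.
- *Stratification is allowed.* Protocol 8.7 makes it optional and SAP 4.4 plans no subgroups.

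Two stronger readings are tempting. A reader might infer that the planned recommendations rest on this dose table. The text does not say so: in SAP 7.2.4 the sentence on recommendations directly follows the multivariate Cox model, whose covariates include dose and regimen. A reader might also infer that changes made before CR dominate the table. The documents give neither a rate of dose changes nor the time on sunitinib after CR in this population, so the proportion is unknown.

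**Conclusion.** The point holds for dose and regimen. One reason in four keeps its own row, the CR-driven reason is among the three merged, and no planned table shows dose or regimen after CR. The first two facts are read directly from the text, subject to the possible damage to the residual reason line. The third rests on a reading of all the outputs in SAP 7.2.2 to 7.2.4.

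The consequence is that a stated secondary objective is not delivered by the table meant to deliver it, and that part of the registry's own question goes unanswered. The continue-or-stop part is not affected. How many changes would be misclassified cannot be estimated from the documents. Because this is a descriptive registry and the underlying data are collected, the defect can be corrected in the table specifications and should be, before the tables are produced.

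**What to change.** In SAP 7.2.3:

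1. Replace the two reason rows with the four reasons of SAP 2.2 plus a residual row. The case report form is not among the documents, so check whether it codes these reasons. If it does not, recode from the reason recorded.
2. Tabulate dose and regimen changes separately before and after CR, and show the dose and regimen in use at CR and the next one recorded after it. First reconcile the two CR dates in SAP Sections 5 and 7.2.4 and use one for the split. Flag changes whose period depends on an imputed date.
3. Add a row for three or more modifications.

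In SAP 7.2.4, replace *to RC* with *before and after CR*.

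The cost is SAP text, a few more table columns, thinner cells with about 90 patients, and possibly some recoding. Item 1 relies on the recorded reason being specific enough to classify. The change concerns reporting only and implies no view on any dose or on clinical management.
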